8. STATISTICAL METHODOLOGY AND STATISTICAL ANALYSES

8.1. Primary Efficacy Analyses

For time to death, treatment comparison will be conducted using Cox proportional hazard regression model.^{4,5} The estimate of the hazard ratio for treatment (sildenafil 80 mg TID/5 mg TID, 80 mg/20 mg TID, and 20 mg TID/5 mg TID) together with its confidence interval (CI) and p-value will be provided. Significance level will be determined using the O'Brien-Fleming approach at each interim analysis and the final analysis. The overall significance level is set at 2.5% (1-sided).

The Cox proportional hazard regression model described above will be conducted using PP population as sensitivity analysis.

Time to death analysis will be conducted by PAH treatment at entry of the study (PAH-treatment naïve vs. on PAH treatment) and etiology of PAH (idiopathic vs. secondary to CTD/surgical repair) based on ITT population and PP population.

The duration of overall survival will be summarized graphically using Kaplan-Meier plots for each of the treatment group. Tabular summaries of the Kaplan-Meier curves giving the median, quartiles, mean, standard error of the mean and range of overall survival will also be provided for each treatment group. Number of events and survival rate at each year will also be tabulated by treatment groups where on-treatment deaths are defined as deaths ≤ 7 days post last study dose.

Analyses will be done based on ITT and PP population. Similar analyses will also be conducted for each level of randomization stratification factors.

For treatment comparison, the exact Logrank test will be conducted as sensitivity analysis using ITT and PP populations.

As described in [Section 4.1](#), time to death secondary analyses will be conducted for treatment comparisons for 80 mg vs. 20 mg, and 20 mg vs. 5 mg. All above analyses/methods will be performed for these two treatment comparisons and are considered secondary analyses of the primary efficacy endpoint (time-to-death).

8.2. Efficacy Analyses for Secondary and Tertiary Endpoints

There will be no p-value adjustment for secondary and tertiary data analyses.

A. Time to First Event of Clinical Worsening

Cox proportional hazard model, analyses using Kaplan-Meier method described above will be used for time to first event of clinical worsening. The analyses will be done using ITT population and PP population for overall subjects and by randomization stratification factors.

In addition, a summary table will be presented showing n(%) of subjects with first qualifying clinical worsening event by event (none, all-cause mortality, non-elective hospital stay for worsening PAH or disease progression) for each study treatment group using ITT and PP population for overall subjects and by randomization stratification factors.

Sensitivity analysis for the secondary endpoint time to first event of clinical worsening will be performed for adjudicated clinical worsening events. All the above described analysis will be conducted.

B. 6MWD

For change from baseline, descriptive summaries (n, mean, SD, 95% CI of the mean, median, and range) will be tabulated at each study visit for each treatment group using ITT and PP population for overall subjects and by randomization stratification factors.

Percent of subjects in each category of 6MWD and change will be tabulated at each study visit for each treatment group using ITT and PP population for overall subjects and by randomization stratification factors. The 95% CI of the percentage will also be tabulated (except for the category of 'missing').

For change from baseline at Month 6 and Month 12, treatment comparisons will be conducted using MMRM with covariates of baseline value, treatment and randomization stratification factors. Least square mean difference, its 95% CI and p-value will be tabulated for each treatment comparison (sildenafil 80 mg TID vs. 5 mg TID, 80 mg TID vs. 20 mg TID and 20 mg TID vs. 5 mg TID).

Analyses will be done based on ITT and PP populations for overall subjects and subgroups by randomization stratification factors.

Figures will be provided for the least square mean change from baseline and 95% CI at Month 12 for each study treatment group for ITT population and PP population for overall subjects and by randomization stratification factors.

C. BORG Score

For change from baseline, descriptive summaries will be tabulated at each study visit for overall and by randomization stratification factors for each treatment group.

The BORG assessment will only be valid for analysis at any specific timepoint if a 6MWT has been performed on the same day. If a BORG assessment is recorded on a different day from the 6MWT then the BORG results for that timepoint will be considered missing.

A non-parametric analysis using stratified Wilcoxon (Van-Elteren) method will be used for treatment comparison at Month 12. The stratified Wilcoxon test will include randomization stratification factors. The median difference and its 95% CI calculated using the Hodges-Lehmann estimator will be presented along with the p-value for the Van-Elteren test for each treatment comparison (sildenafil 80 mg TID vs. 5 mg TID, 80 mg TID vs. 20 mg TID and 20 mg TID vs. 5 mg TID). The analyses will be done for ITT population for overall subjects.

D. WHO Pulmonary Hypertension Functional Class

The number and percentages of subjects with each WHO pulmonary hypertension functional class will be tabulated by study visit, for overall and by randomization stratification factors for each treatment group. In addition, a table will be presented by study visit showing number and percentages of subjects improving by at least 2 classes, improving by 1 class, not changing, worsening by 1 class, worsening by at least 2 classes, discontinued, died or missing. The table will be presented for overall and by randomization stratification factors for each treatment group.

The analyses will be done for ITT population for overall subjects and by randomization stratification factors.

8.3. Summary of Efficacy Analyses

Endpoint	Analysis Set	Subgroup Analyses ²	Statistical Method
Time-to-death ¹	ITT and PP	Yes	Cox proportional hazard regression
Time-to-death	ITT and PP	Yes	Kaplan-Meier for overall survival
Time-to-death	ITT and PP	Yes	Exact LogRank
Time-to-first event of clinical worsening	ITT and PP	Yes	Cox proportional hazard regression
Time-to-first event of clinical worsening	ITT and PP	Yes	Kaplan-Meier
Clinical worsening	ITT and PP	Yes	Descriptive: n (%) of each qualifying first event
6MWD change	ITT and PP	Yes	MMRM for Month 6 and 12
6MWD change	ITT and PP	Yes	Descriptive: summary statistics by study visit
6MWD change	ITT and PP	Yes	Descriptive: n (%) of each change category
6MWD	ITT and PP	Yes	Descriptive: n (%) of each category
BORG score change	ITT	No	Stratified Wilcoxon & Hodge-Lehmann estimates for Month 12
BORG score change	ITT	Yes	Descriptive: summary statistics by study visit
WHO pulmonary hypertension functional class	ITT	Yes	Descriptive: n(%) of each class and n(%) by each change category by study visit

¹ Primary analysis.

² By randomization stratification factor.

8.4. Safety Analyses

The following data will be summarized and listed by treatment and in accordance with the current Pfizer data standards: adverse events (all causality and study treatment related), concomitant medication, discontinuation, laboratory data, vital signs, and physical examination.

The following data will be listed by treatment and in accordance with the current Pfizer data standards: serious adverse events, death, ECG, and pregnancy test.

For treatment duration, descriptive summary statistics (n, mean (standard deviation), and median (range)) will be tabulated. In addition, n(%) of subjects will be calculated for the following categories of treatment duration:

- <1 year;
- 1-<2 years;
- 2-<3 years;
- 3-<4 years;
- 4-<5 years;
- 5-<6 years;
- 6-<7 years;
- >7 years.

For tier-1 and tier-2 treatment emergent adverse events, the risk assessment will be based on incidence proportions. For a given treatment group and event type, the incidence proportion is defined as the number of subjects having at least one event divided by total number of subjects in the safety population. In the case of events with zero counts, the incidence proportion will be zero.

Incidence proportion and its 95% CI will be tabulated for each tier-1 and tier-2 event by treatment group. For each treatment comparison (sildenafil 80 mg TID vs. 5 mg TID, 80 mg TID vs. 20 mg TID and 20 mg TID vs. 5 mg TID), difference in incidence proportion (risk difference [RD]) and its 95% CI will be produced. For tier-1 events, proportion in each treatment, 95% CI and p-values for treatment comparison will also be produced for each of the following safety topics (eye disorders, deafness, cardiovascular (rhythm abnormalities, cardiac failure, and myocardial infarction), cerebrovascular, and pregnancy-related). The specific MedDRA PTs describing each of these safety topics are contained in the Revatio Safety Review Plan (Target Medical Event [TME] List). The p-value and 95% CIs of the RD will be estimated using unconditional exact binomial methods.

The p-values and 95% CIs will not be adjusted for multiplicity (this should be noted via a footnote in the tables). Caution in interpreting the results should be taken for this reason and given the exploratory nature of these analyses.

In addition, a two-panel plot will be presented for tier-1 and tier-2 events. The left panel gives the proportions of AEs observed in each treatment group while the right panel displays 95% CI for the risk difference for each AE for each treatment comparison.

For the graphic display for tier-1 events, proportions of each safety topic in each treatment, its 95% CI and P-Value for each treatment comparison will be added.

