Pfizer submitted the Revatio Oral Suspension New Drug Application (NDA) to the Food and Drug Administration (FDA) for the pediatric indication in November 2011. On 30 August 2012, the FDA approved the NDA for the oral suspension, but did not approve the pediatric PAH indication for Revatio. The FDA has introduced the following warning in the United States Package Insert (USPI): “In a long-term trial in pediatric patients with PAH, an increase in mortality with increasing Revatio dose was observed. Deaths were first observed after about 1 year and causes of death were typical of patients with PAH. Use of Revatio, particularly chronic use, is not recommended in children.” FDA also issued a Drug Safety Communication (DSC) which includes a description of this information from the revised Revatio USPI. A DSC is a specific tool used by the FDA to communicate important information to the public about safety issues, including emerging safety information, about marketed drugs. As a consequence of the finding of a dose-related increase in mortality in pediatric patients with PAH, FDA has asked Pfizer to evaluate the effect of sildenafil on the risk of death in adults with PAH at three dose levels, namely 5 mg, 20 mg and 80 mg TID.

Dose regimens for this trial will be 5 mg, 20 mg and 80 mg TID. The rationale for inclusion of the 5 mg dose in this trial is that the minimum effective dose of sildenafil in adults with PAH is not known. Therefore, it is important to evaluate whether doses lower than 20 mg TID might be similarly effective and relatively safer than the current recommended dose of 20 mg TID when used for the long-term treatment of adult PAH. The rationale for inclusion of the 80 mg TID dose is that, while the current US label does not recommend sildenafil at doses above 20 mg TID, it is known from prescribing practices that some adult patients with PAH are prescribed doses up to 80 mg TID. Therefore, it is important to determine whether the use of doses higher than the approved dose might be less safe than the current recommended dose.

This study will evaluate the relative effects of sildenafil on mortality when administered at the three doses indicated above in adults with PAH. In addition, the relative effects on clinical worsening and 6-minute walking distance (6MWD) will also be assessed.

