6.2. Safety Endpoints

A. Treatment-emergent Adverse Events (AE)

A treatment-emergent AE is an AE with an onset after initiation of study treatment, or an AE present at initiation of study treatment that subsequently worsens (ie, increases in severity or relationship to study treatment).

A 3-tier approach will be used to summarize treatment-emergent AEs. Under this approach, AEs are classified into 1 of 3 tiers. Different analyses will be performed for different tiers (See [Section 8.4](#)).

Tier-1 events: These are pre-specified events of clinical importance and are maintained in a list in the product's Safety Review Plan.

Tier-2 events: These are events that are not tier-1 but are "common". A MedDRA PT is defined as a tier-2 event if there are at least 5% in any treatment group.

Tier-3 events: These are events that are neither tier-1 nor tier-2 events.

B. Other Safety Endpoints

- Serious AE (SAE);
- Death;
- Concomitant medication;
- Subject discontinuation;
- Vital signs;
- Laboratory results;
- Physical examination;
- Duration of treatment.

For non-efficacy endpoint, study follows protocol screening definition (see Section 6.1 in protocol).

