9.1. Sensitivity Safety Analysis

If a subject is switched from 5 mg to 20 mg, they will be reported under their randomized treatment group for all efficacy analyses but will be reported under the treatment they first receive for all safety analyses. In addition, a sensitivity safety analysis for deaths, major AE and SAEs will be conducted on the subgroup of subjects that switched from 5 mg to 20 mg only.

In summary, study analyses tables will present data by treatment as follows:

- All efficacy analysis will be presented with 3 randomized arms (5 mg, 20 mg, 80 mg).
- All safety analysis will be presented with 3 actual treated arms (5 mg, 20 mg, 80 mg).
- Sensitivity analysis for the subgroup of patients who switch from 5 mg to 20 mg, for major safety endpoint (ie, deaths, AEs, SAEs) will be presented with 4 treated arms (5 mg, 20 mg, 80 mg, 5-20 mg).

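### SAP 8.4 lists serious adverse events without a three-arm summary, and the only by-arm SAE display (SAP 9.1) has no stated statistic and an unclear scope

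*SAP*

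**What the plan says.** SAP 6.2 B includes serious adverse events among the other safety endpoints. SAP 8.4 opens with two adjacent sentences. The first covers data that will be "summarized and listed by treatment and in accordance with the current Pfizer data standards: adverse events (all causality and study treatment related"), together with concomitant medication, discontinuation, laboratory data, vital signs and physical examination. The second covers data that "will be listed by treatment and in accordance with the current Pfizer data standards: serious adverse events, death, ECG, and pregnancy test".

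The same section then plans between-arm comparisons for tier-1 and tier-2 treatment-emergent events. For 80 vs 5, 80 vs 20 and 20 vs 5 mg, the "difference in incidence proportion (risk difference [RD]) and its 95% CI will be produced", using unconditional exact binomial methods and without multiplicity adjustment. Tier 1 is a pre-specified list. Tier 2 is set by frequency: "A MedDRA PT is defined as a tier-2 event if there are at least 5% in any treatment group" (SAP 6.2).

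SAP 9.1 adds a sensitivity analysis for subjects switched from 5 to 20 mg, which "for major safety endpoint (ie, deaths, AEs, SAEs) will be presented with 4 treated arms": 5, 20, 80 and 5-20 mg. Protocol 9.4 tabulates the incidence and rate of each treatment-emergent event, also by severity and relationship. It does not mention seriousness.

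**The concern.** The protocol summary justifies the 80 mg arm by saying that "it is important to determine whether the use of doses higher than the approved dose might be less safe than the current recommended dose". After death, SAEs are the broadest measure of serious harm that the trial collects. The SAP makes them an endpoint but gives them a weaker presentation than ordinary adverse events: a listing, with no count or comparison by dose in the main safety analysis.

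If the SAP is followed as written, the study report need contain no three-arm SAE proportion and no interval for a dose difference in SAEs. Any such figure would then be produced after unblinding, with the choice of events, denominators and method still open.

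**Working it through.** No figure in the plan is at issue, so the main check sets the relevant sections side by side.

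**1. Where SAEs are dealt with**

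| Section | SAE content |
|---|---|
| SAP 6.2 B | Named as a safety endpoint |
| SAP 8.4, opening sentences | Listed by treatment; adverse events are summarised and listed |
| SAP 8.4, tier analyses | Tiers set by list or frequency, not seriousness; no any-SAE row |
| SAP 9.1 | Four treated columns; no statistic, interval or test stated |
| Protocol 9.4 | Incidence, rate, severity and relationship; seriousness absent |

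No section specifies a three-arm SAE proportion, difference or interval.

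**2. Whether SAP 9.1 fills the gap**

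Its text says the analysis is done only on the subgroup that switched; its summary list describes four treated arms. These scopes differ. If the 5 mg and 5-20 mg columns are mutually exclusive (the natural reading, though not stated), the randomised 5 mg arm is divided by a later event. Under Protocol Appendix 6, a switcher had to be alive, still on study treatment at the visit due before 15 August 2020, at a site with no post-study option, and willing to continue. A 5 mg column without these subjects is a selected group. The direction of the effect on SAEs cannot be determined from the documents, because switchers survived longer but also had more time to accrue events.

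**3. Whether the tier comparisons fill the gap**

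The tier-2 threshold at 143 per arm is 0.05 × 143 = 7.15, so 8 subjects in one arm are needed (8/143 = 5.6%). A term outside the tier-1 list that affects 7 subjects in one arm (7/143 = 4.9%) and none in another is tier 3, and gets no risk difference or interval, however serious the cases. Serious harm spread over several such terms is not compared; an any-SAE row would pick it up.

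**4. Precision of the missing comparison (illustration)**

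Inputs: n = 143 per arm (Protocol 9.1, planned); SAE proportion p is an assumption, because the documents give none.

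- 95% half-width = 1.96 × √(2p(1−p)/143). At p = 0.30: 1.96 × √(0.42/143) = 1.96 × 0.0542 = 0.106.
- Detectable increase d: the smallest d with 80% power at two-sided 5%, where power = Φ((d − 1.96·SE₀)/SE₁). SE₀ uses the pooled proportion and SE₁ the separate proportions.

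| Assumed p | Half-width (points) | Detectable increase (points) |
|---|---|---|
| 20% | 9.3 | 14.8 |
| 30% | 10.6 | 16.1 |
| 40% | 11.4 | 16.5 |
| 50% | 11.6 | 16.3 |
| 60% | 11.4 | 15.5 |

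These are normal approximations. The exact method in SAP 8.4 would give somewhat different limits.

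**The case against.** A reader might infer that SAEs appear nowhere except in a patient listing, or that a dose difference in SAEs could not be estimated. The documents do not support either reading. SAP 9.1 presents SAEs by arm. Its 20 and 80 mg columns are whole, and if the two 5 mg columns are disjoint, adding them restores that arm. The 8.4 listing is by treatment, so with arm denominators the proportions could be counted from it. What is missing is a planned estimate, not the data.

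Much serious harm is also compared elsewhere. Death has a Cox hazard ratio for all three dose pairs (SAP 8.1). Clinical worsening, which includes hospital stay for worsening PAH, is analysed with the same methods (SAP 8.2). The tier-1 topics, including cardiac failure, myocardial infarction and cerebrovascular events, get proportions, intervals and p-values. Serious cases also count within any tier-1 or tier-2 term. All of this stands and narrows the gap.

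The sponsor's data standards, cited in both 8.4 sentences, might include an SAE summary. That cannot be settled from the documents. The same phrase governs both sentences, so it does not remove the difference between them.

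Two limits on the remedy also stand. Protocol 8.6.1 first says that death and clinical worsening are not to be reported as SAEs unless judged causally related, then that all SAEs will be reported as such. An any-SAE proportion therefore depends on how endpoint events are counted. A crude proportion also takes no account of unequal follow-up.

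**Conclusion.** The point holds in a limited form. SAP 8.4 chooses a listing for a named safety endpoint while summarising adverse events in general. The only stated by-arm SAE presentation is a switch-related sensitivity display with no stated statistic and an inconsistent scope. The missing items are an overall SAE estimate by dose and SAEs by system organ class and preferred term, including serious events spread over uncommon terms.

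This should be corrected because it bears on whether higher doses are less safe. It does not affect the primary mortality analysis, and it shows no bias in any planned result. The interval of roughly ±11 points for SAE proportions of 30% to 50% rests on an assumed rate and the planned arm size. It describes what the added table could show: a usable but fairly coarse comparison, with 80% power only for increases of about 15 to 16.5 points over the 20% to 60% range.

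**What to change.** In SAP 8.4:

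- Move serious adverse events to the summarised-and-listed group.
- Tabulate n (%) of subjects with at least one SAE, overall and by system organ class and preferred term, in the three treated arms used for the other safety analyses.
- For any SAE, give the risk difference and 95% CI for 80 vs 5, 80 vs 20 and 20 vs 5 mg by the unconditional exact method already planned, under the existing multiplicity footnote.
- State whether deaths and clinical worsening events sent to adjudication are included, for example by showing the table with and without them, and reconcile this with the two statements in Protocol 8.6.1.

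In SAP 9.1, keep the four-column table as the sensitivity display. State its population, its statistic and whether the 5 and 5-20 mg columns are mutually exclusive.

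The cost is a few SAP sentences and one table, shown in two versions if endpoint events are separated, from data already collected. The drawback is a few more unadjusted exploratory intervals.

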8.2. Reporting Period

For SAEs, the active reporting period to Pfizer or its designated representative begins from the time that the subject provides informed consent, which is obtained prior to the subject's participation in the study, ie, prior to undergoing any study-related procedure and/or receiving investigational product, through and including 28 calendar days after the last administration of the investigational product. Serious adverse events occurring to a subject after the active reporting period has ended should be reported to the Sponsor if the investigator becomes aware of them; at a minimum, all serious adverse events that the investigator believes have at least a reasonable possibility of being related to study drug are to be reported to the Sponsor.

AEs (serious and non-serious) should be recorded on the case report form (CRF) from the time the subject has taken at least one dose of study treatment through the last subject visit.

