9.4. Safety Analysis

Safety analyses will be carried out for the ITT population. All adverse events will be coded and grouped by system organ class. The incidence and rate of each treatment emergent adverse event will be tabulated by treatment. Tabulations by maximum severity and relationship to study treatment will also be included.

Vital signs and safety laboratory data will be explored through the use of standard presentations of descriptive statistics.

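### Adverse events are compared only by crude proportions in a multi-year trial; the rate named in the protocol is never defined, and at-risk time may be shorter on 5 mg.

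*SAP*

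**What the plan says.** SAP 8.4 sets the measure for tier-1 and tier-2 treatment-emergent events: "the risk assessment will be based on incidence proportions". The proportion is defined as "the number of subjects having at least one event divided by total number of subjects in the safety population". Pairwise risk differences follow for the three dose comparisons. On their inference the SAP says: "The p-value and 95% CIs of the RD will be estimated using unconditional exact binomial methods". The two-panel plot shows the same quantities.

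Exposure appears once, as description: "For treatment duration, descriptive summary statistics (n, mean (standard deviation), and median (range)) will be tabulated". Yearly categories are added, but duration does not enter the event comparison.

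Protocol 9.4 names two measures: "The incidence and rate of each treatment emergent adverse event will be tabulated by treatment". Neither document defines the rate, and SAP 8.4 contains none.

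For the main safety analysis, SAP 8.4 provides listings by treatment for "serious adverse events, death, ECG, and pregnancy test". SAP 9.1 adds a four-arm sensitivity display covering deaths, adverse events and serious adverse events, with switched subjects as the fourth group. In the main safety tables those subjects stay under the treatment they first received, which is 5 mg.

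On the window, SAP 6.2 says: "A treatment-emergent AE is an AE with an onset after initiation of study treatment". It gives no end. Protocol 8.2 runs active reporting of serious events "through and including 28 calendar days after the last administration of the investigational product". After treatment stops, the protocol's schedule for discontinued subjects collects adverse events at the end-of-treatment visit and the 28-day check. After that it collects survival only.

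**The concern.** A crude proportion compares arms fairly when subjects are observed for similar lengths of time. Here observation lasts years, and adverse-event collection effectively ends with death or soon after treatment stops. An arm with more deaths or earlier discontinuation has less time in which to record a first event, so at equal underlying hazards its proportion is lower.

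The affected arm would probably be 5 mg. The protocol (1.1) asks whether lower doses might be relatively safer and wants the adverse-event profile of doses above the approved one. A crude comparison could slightly flatter 5 mg and slightly disadvantage 80 mg on the tier-1 topics, with p-values attached and no companion measure to expose the artefact.

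**Working it through.** **No plan figure to reproduce.** The safety section states no number. The exposure model can be checked against the design instead. With 15% mortality at 2 years, h = −ln(0.85)/2 = 0.0813 per year. Accrual of 429 at 100 per year takes 4.29 years. Reading the 20% drop-out as spread over 7.7 years gives −ln(0.80)/7.7 = 0.029 per year. This model gives 143.2 expected deaths at 7.7 years, against the planned 143.

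**Is unequal exposure plausible?** Protocol 9.5 requires one-sided p < 0.0015 (z = 2.968) against a hazard ratio of 2 at the 50% look. With SE(log HR) ≈ 2/√D, the estimated HR (80/5) must lie below exp[ln 2 − 2.968 × 2/√D].

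- D = 48 (assumed two-thirds of the 72 deaths): exp(0.693 − 0.857) = 0.85.
- D = 72 (all deaths in the two compared arms, the extreme case): exp(0.693 − 0.700) = 0.99.

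Protocol Appendix 6 says non-inferiority was met. If the planned boundary was applied, estimated mortality was therefore higher on 5 mg.

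**Effect on crude proportions.** Inputs: other discontinuation d = 0.03 per year (assumed), follow-up u uniform from 7.7 − 4.29 = 3.41 to 7.7 years, and the same constant adverse-event hazard a in both arms. The reference arm has mortality 0.0813 per year; the other arm has r times that. With k = mortality + d, averaging over u:

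- mean exposure = (1 − e^(−ku))/k
- crude proportion = a/(a+k) × (1 − e^(−(a+k)u))

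| Mortality ratio r | Corresponding HR 80/5 | Mean exposure (y) | Crude % at a = 0.05 / 0.10 / 0.20 | Spurious gap vs reference (points) |
|---|---|---|---|---|
| 1.00 (reference) | 1.00 | 4.10 | 18.1 / 32.2 / 52.0 | 0 |
| 1.18 | 0.85 | 3.95 | 17.5 / 31.2 / 50.5 | 0.6 / 1.0 / 1.5 |
| 1.43 | 0.70 | 3.75 | 16.7 / 29.8 / 48.5 | 1.4 / 2.4 / 3.5 |
| 2.00 | 0.50 | 3.36 | 15.0 / 27.0 / 44.5 | 3.1 / 5.2 / 7.5 |

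First events divided by person-years to first event return a exactly in every row, because a was made constant.

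For a given u, the gap between arms grows with u. Follow-up shorter than the 7.7-year plan would therefore shrink these figures.

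**Does the rate always repair it?** Take identical early-clustering hazards in both arms (assumed 1.2 per year for 3 months, then 0.02 per year) with mortality doubled in one. The crude proportions are about 30% in the shorter-exposure arm and 31% in the other. The rates are 12.3 and 10.6 per 100 patient-years, a spurious ratio of 12.3/10.6 = 1.16 *against* the shorter-exposure arm. For such events the proportion is the better of the two measures.

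**The case against.** Much of the case on the other side stands.

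- A reader might infer that exposure is known to differ by arm. It is not. No arm-level duration is given, the design assumes equal mortality, and staggered entry is balanced by randomisation. Only differential death or discontinuation can create the bias.
- A reader might say the trial was stopped because of mortality in one arm. Protocol Appendix 6 and SAP 9 give the met primary objective first and the 5 mg concern second.
- A reader might conclude that the trial's main safety question is confounded. The regulator's question was mortality, which SAP 8.1 analyses by Cox, Kaplan-Meier and exact log-rank methods. Clinical worsening is also a time-to-event analysis. The adverse-event comparisons are labelled exploratory, with advice to be cautious, although that advice concerns multiplicity and not exposure.
- Serious events are not confined to listings. SAP 9.1 includes them in its four-arm display, and a serious event whose term falls in tier 1 or 2 is already counted there. What is missing is a comparative summary of serious events in the main three-arm tables.
- The SAP supplements the protocol, so the protocol's rate is not withdrawn. It is left undefined and unimplemented.
- The treatment-duration table would let a reader see an imbalance, but not adjust for it.
- Keeping post-switch time under 5 mg lengthens that arm's window and works in the opposite direction, by an amount the documents do not allow one to estimate.

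**Conclusion.** The gap in the plan is real and its likely effect is modest. SAP 8.4 offers only crude proportions for comparing adverse events, and the rate in protocol 9.4 has no definition or table behind it. Shorter at-risk time on 5 mg is a reasonable inference from the interim result, not a documented fact.

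Under the stated assumptions, mortality alone would shift a comparison by 0.6 to 1.5 points at a ratio of 1.18 and by 1.4 to 3.5 points at 1.43. The larger range of about 3 to 7 points requires doubled mortality over the full 7.7-year plan and should not be presented as expected. Unequal discontinuation could add to or reduce these figures; the documents give no basis for sizing it.

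The stronger remedy, replacing proportions by rates, is not supported either. With early-clustering events the rate can mislead in the opposite direction. The two measures belong side by side, so this is a worthwhile, low-cost improvement to the safety analysis. It does not touch the primary mortality conclusion.

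**What to change.** Amend SAP 8.4 as follows, keeping the crude proportions and risk differences.

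1. Report person-years at risk by arm.
2. For tier-1, tier-2 and serious adverse events in the main three-arm tables, add exposure-adjusted incidence rates (subjects with a first event per 100 patient-years at risk). Give rate differences or ratios and 95% CIs for the three pairwise comparisons. State that this is the rate meant in protocol 9.4.
3. For tier-1 safety topics and serious adverse events, add time-to-first-event summaries (cumulative incidence, with death as a competing event), which also show whether a constant hazard is tenable.
4. In SAP 6.2, state when the treatment-emergent window ends. In SAP 9.1, state how events and person-time after the 5-to-20 mg switch are counted.

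The cost is SAP wording and one further set of tables from data already collected. The drawback is that rates assume a roughly constant hazard and can mislead for events that cluster early. They should therefore supplement the proportions and be read with the cumulative-incidence curves.
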